- Ventilator-collected parameters during the therapy night such as: Mean EPAP, Respiratory Rate, Minute Ventilation, and ΔX_{rs} values.
- Ventilator-collected parameters during the EFL screening; ΔX_{rs} value, % flow limited breaths, mask leak values.
- SpO_2 .
- Patient Therapy comfort assessment via Questionnaires

Study Design:

This study is a nonrandomized, unblinded overnight engineering clinical evaluation of the Vector NIV device in COPD patients with EFL. Up to 50 individuals may be enrolled in order to have a total of up to 30 completed participants. Male and female participants who qualify per the inclusion/exclusion criteria may be enrolled.

Potential participants will be identified and recruited from the site database of COPD patients. Potential participants may also be identified by a local marketing company. These participants will complete online or phone screenings prior to being seen at the clinical site.

Schedule of Events:

Participants will be contacted by designated study staff from the site database of COPD patients. Participants may be pre-screened over the phone to determine eligibility. Participants that are interested will be scheduled for the screening visit at the clinical office.

Potential participants may be also be found by a local marketing company. This marketing company will utilize their local database to find potential participants in the Pittsburgh, PA area. These participants will undergo a brief online and/or over the phone screening by the marketing company. If they are found to be potentially eligible, Philips Respironics study staff will reach out to the participants. A more thorough phone screen will be conducted by the Philips Respironics study staff. If the person is still found to be potentially eligible for the study and is interested they will either be scheduled by the Philips Respironics staff to come into the Pittsburgh Pulmonary Physician Practice site or will be contacted by the staff of Consolidated Clinical Trials for appointment scheduling. A waiver of informed consent for screening will be submitted to the IRB for contacting these participants.

Study Visit 1 (screening)

Once the participant arrives, the study will be explained in full detail. If the participant agrees, he/she will be consented into the study and the participant will be given a copy of the informed consent.

Once consent is obtained and eligibility is confirmed, the following study related procedures will be conducted:

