During the Sleep study, the Vector NIV device will be connected to a laptop computer where all Ventilator related parameters collected by the device can be viewed and monitored by the sleep technician and the Philips Respiration engineer. These outputs include the device IPAP and EPAP pressures, EFL value, patient flow, mask leak, minute ventilation, and respiratory rate. A flexible finger sensor will be placed on the finger in order to measure and monitor oxygen saturation

During the sleep study, the Vector NIV device with the optimized EPAP will be tested in periods with both fixed pressure support as well Average Volume Assured Pressure Support during the night. In the event that the study participant presents with any obstructive or respiratory related events during the sleep study during the Vector therapy, the trained sleep technician will be able to make manual adjustments to the device pressure settings in order to address the issue (Appendix A).

In the event that manual titration was unsuccessful, the trained sleep technologist will refer to standard of care procedures including, but not limited to, switching to a backup device that the sleep lab has available.

Comfort Assessments: At the end of the sleep study (within two business days) all participants will be asked to complete a comfort questionnaire via phone. This call will

Engineering Evaluation of the Vector NIV Device in Chronic Obstructive Pulmonary Disease (COPD) Patients be conducted by the sponsor study staff. This phone call should last less than 10 minutes.

Study participants who complete the overnight sleep study successfully and are interested, will be asked to take part in the two week home use sub study. If the participant agrees to participate, they will receive one on one training on the Vector NIV device and accessories by clinical study staff and/or Philips engineers. They will also be given a device user manual. Once trained on the device, study participants will be asked to take the device home and use as instructed during the night for a 2 week period. Study participants will be given the mask that was used for the overnight sleep study to use with the Vector NIV device for the 2 week period.

-Optional Exit Interview and/or EFL assessment – (within 5 months of visit 1)

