The purpose of this engineering study is to collect engineering and subjective data on the Vector device. No formal statistical analysis is planned. Any deviations to this approach will be indicated in either a revised protocol or in the study report. Baseline and questionnaire ratings will be summarized with descriptive statistics: continuous data will be presented as averages and standard deviations, and categorical data will be presented as frequencies and percentages.

Participant Disposition

Participant disposition, including the total number of participants enrolled, completed, early terminations and withdrawals, will be presented. A listing will be provided with the reasons for discontinuation.

Safety Analysis

Safety evaluations will be performed by recording clinical adverse events at the time originally reported as a part of the study visits. Adverse events will be provided in data listings.

Interim Analysis

Since this is an engineering evaluation, data will be reviewed during the course of the study, but a formal interim analysis does not apply.

Direct Access to Source Data / Documents

Only site clinical study staff and approved Philips staff working with the research will know the identity of the participants. All information recorded by the study team and provided for analysis will be given a study ID number.

Privacy rules and requirements according to federal and state governing regulations will be implemented. All the information collected as part of this study will be kept confidential. All information collected for this study will be kept in a secured area or stored in a password protected computer if digital. Except when required by law, participants will not be identified by name, social security number, address, telephone number, or any other direct personal identifier in study records. For records disclosed to Philips Respiration participants will be assigned a unique code number.

Results of the study related data, medical history, and information obtained from the questionnaire and device data will be reported and received by Philips Respiration. Philips Respiration will use participant study data for research purposes to support engineering objectives described in this protocol.

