Data queries will be addressed by delegated study personnel and CRF/ eCRFs will be reviewed and signed off by PI prior to study closure. Monitoring will be completed in accordance with US FDA CFR, as applicable.

Ethics

This study will be submitted and reviewed by the Allendale Review Board. All participants will be consented prior to completing the trial. The Primary Investigator will review all adverse events as it relates to the study device.

This study will receive approval and oversight from
Allendale Institutional Review Board
[name]
[name]
United States
[contact]

All data will be kept confidential and in a secure location if on paper or on a secure server or device. Only approved study personnel will have access to study related

Engineering Evaluation of the Vector NIV Device in Chronic Obstructive Pulmonary Disease (COPD) Patients documents. All electronic data shall be stored in a coded data set. All paper documents shall be kept in a secure area. Study data and source will be made available for study related monitoring or audits by the IRB/IEC, sponsor, or regulatory inspection(s). Results of the study related data, and information obtained from the engineering study, will be collected, received and reported by Philips Respironics. Philips Respironics will use participant study data for research purposes to support scientific and marketing objectives described in this protocol.

Data Handling and Recordkeeping

Hard copies of the study will be kept on site for at least 2 years after study completion. The sponsor will maintain study records indefinitely. Records will be stored at Iron Mountain, a secure information management services company.

Financing and Insurance

If the participant is injured during the course of the trial and as a direct result of this trial, they should contact the Principal Investigator, [name]. The participant will be directed to seek clinically appropriate medical care for that injury. However, we cannot guarantee that the medical care and treatment will be provided without charge or that it will be paid for by the participants insurance company, and the costs incurred may ultimately be the participant's responsibility.

Registration on ClinicalTrials.gov or other applicable registry

As this is engineering clinical evaluation, this will not be registered on ClinicalTrials.gov or other applicable registry.

Risk and Benefit Analysis

Potential Risks and Discomforts

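### The overnight comfort rating is collected by phone by sponsor staff up to two business days after the night, with no described safeguard against favourable-response or recall bias; collecting it in the lab is a cheap improvement

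*Combined protocol and SAP*

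**What the plan says.** Study Endpoints lists four items, the last being "Patient Therapy comfort assessment via Questionnaires". Study Design describes the study in these terms: "This study is a nonrandomized, unblinded overnight engineering clinical evaluation of the Vector NIV device in COPD patients with EFL". No comparator is described.

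The Comfort Assessments paragraph under Study Visit 2 sets the timing ("At the end of the sleep study (within two business days") and the mode: "all participants will be asked to complete a comfort questionnaire via phone". It adds that the call will "be conducted by the sponsor study staff" and should take less than ten minutes.

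Statistical Methods, General Considerations, states: "No formal statistical analysis is planned". It then commits to one kind of summary: "Baseline and questionnaire ratings will be summarized with descriptive statistics", with averages and standard deviations or frequencies and percentages. The Ethics section says that the sponsor will use the data "to support scientific and marketing objectives described in this protocol".

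**The concern.** The participant tells an employee of the manufacturer, aloud, how comfortable the manufacturer's device was. People asked in this way may soften criticism. With no blinding and no comparator, a shift of that kind cannot cancel against another arm; it passes straight into the reported mean or percentage.

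The delay adds a second, separate risk. The participant has to recall a night that included periods of fixed pressure support and of volume-assured pressure support, and possibly manual adjustments or a change to a backup device. A participant who agrees to the home-use sub-study may also have used the device at home before the call, so the answer could mix the two experiences.

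At stake is how far the overnight comfort summary can be read as a description of that night.

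**Working it through.** The plan gives no figure on this point, so the check is to set the sections side by side. The only arithmetic is a count of days.

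1. **Is comfort an endpoint?** Yes. It is one of the four bullets under Study Endpoints.

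2. **Does the plan commit to reporting it?** Yes, as part of a class. General Considerations gives descriptive statistics to baseline data and questionnaire ratings. Baseline data are not an outcome. Disposition is to be presented but is not an endpoint, and adverse events are only listed. The section states no summary for the ventilator parameters, ΔXrs, SpO2 or sub-study adherence. Assessment of Performance names ventilator parameters as the basis for judging the device but gives no summary statistic. Questionnaire ratings are therefore the only class of listed endpoint with a stated summary.

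3. **Who collects it, and is there a safeguard?** Sponsor study staff, by phone. The documents available describe no self-completion, independent interviewer or script for this questionnaire, and no rule for participants who cannot be reached. The instrument, its scale and its scoring direction are not shown either, and may lie in redacted pages.

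4. **How long can the delay be?** Two business days is a maximum. Ignoring public holidays:
   - Night ends Wednesday morning: Thursday is day 1 and Friday is day 2, so the limit is 2 calendar days.
   - Night ends Friday morning: Monday is day 1 and Tuesday is day 2, so the limit is 4 calendar days.

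5. **Can home use come before the call?** Study Visit 2 says that interested completers will be trained and then take the device home, but gives no start date. If the device went home on the Friday morning, the nights of Friday, Saturday, Sunday and Monday (4 nights) could precede a Tuesday call. If home use starts after the call, the number is 0. The sub-study's own screening visit may also delay the start. The overlap is possible but not established, and nothing in the text rules it out.

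6. **Is collection in the lab feasible?** The participant is in the sleep lab until the normal wake-up time, so a form can be completed before leaving. A sponsor engineer helps to prepare the participant and monitors the night, so moving the form to the lab does not by itself remove sponsor presence.

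**The case against.** The strongest reply is that little depends on comfort. The primary objective is to collect engineering data, neither study hypothesis concerns comfort, and no formal analysis, success criterion or decision rule uses it. All of that stands, and it limits how serious the point can be.

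The marketing wording also needs its context. It covers objectives described in the protocol, and the marketing use actually described is the optional videotaped interview or screening session, with consent. Another section speaks of engineering objectives, and no publication is planned. The wording shows that the sponsor has an interest in the answers; it does not show that comfort ratings will be used in promotion.

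The fix is also imperfect. The protocol itself warns of poor sleep and next-day sleepiness, which could affect a morning rating. Coding the forms gives limited protection, because approved sponsor staff know participants' identities and may have phone-screened them. Both points stand. They are reasons to keep the sponsor engineer away from completion and to state the sleepiness downside, but they do not favour the sponsor call.

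A reader might also infer that comfort ratings cannot be compared with the other questionnaires because the setting differs. No such comparison is planned. The documents do not say whether the Visit 1 forms are self-completed, and the home-use survey covers a different exposure. Nothing in the plan turns on that difference.

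**Conclusion.** The point holds as a cheap improvement. As written, the plan leaves the overnight comfort ratings open to favourable-response and recall bias and, for participants who enter the sub-study, possibly to the influence of home nights. The worst consequence is an over-favourable descriptive mean or percentage. No test is invalidated, because none is planned.

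Three stronger readings are tempting and are not supported:

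- **That the ratings are biased upward.** Favourable answering is a credible risk, but the documents show neither its direction nor its size. Recall error has no determined direction. Without the scale, it is not known whether a higher score is the favourable one.
- **That the bias would exceed sampling error.** This would need a scale, a standard deviation and an assumed shift. The documents give none of these, and the answer changes with the values chosen.
- **That this call is the only outcome to be summarised.** Questionnaire ratings can also cover the Visit 1 questionnaires and the sub-study comfort questionnaires or survey, none of which is described as a sponsor phone call.

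The conclusion assumes that no safeguard exists in text that is not visible, such as a questionnaire script. The possible overlap with home use also depends on the start date, which is not stated.

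**What to change.** In the Comfort Assessments paragraph under Study Visit 2, replace the sponsor call with self-completion. Participants fill in the same questionnaire on paper in the sleep lab, after waking and before leaving, without the sponsor engineer present. They hand the form to site staff, who record it under the study ID.

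Keep a phone call only as a back-up for missing forms. Site staff make it before any home use starts, and responses obtained that way are flagged in the data and in the summary.

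The cost is protocol wording and a few minutes at discharge in place of a call of up to ten minutes. It needs no extra visit and leaves the device procedures unchanged. The downside is that some participants may be sleepy when they answer, and scores may be slightly less favourable than those given by phone. The change assumes that the questionnaire, which is not shown, can be used on paper.

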FOT: Forced Oscillation Technique – A method to detect the presence of expiratory flow limitation.

FVC: Forced Vital Capacity – Spirometry measurement in which the patient inhales maximally and then exhales as rapidly and completely as possible.

IPAP: Inspiratory Positive Airway Pressure - Physician prescribed pressure for the inspiratory (breathing in) phase of an individual on Bi-level PAP therapy.

Noninvasive Positive Pressure Ventilation (NPPV): mechanical ventilation provided noninvasively (by mask or similar interface) rather than through an endotracheal tube or tracheostomy.

Positive End Expiratory Pressure (PEEP): Pressure in the lungs (alveolar pressure) above atmospheric pressure (the pressure outside of the body) that exists at the end of expiration.

OSA: Obstructive Sleep Apnea - a disorder in which complete or partial obstruction of the airway during sleep causes loud snoring, oxyhemoglobin desaturations and frequent arousals.

S Mode: Spontaneous Ventilation – provides ventilation in synchrony with a person's spontaneous breathing efforts; triggering of a breath cycle is only by the patient.

S/T Mode: Spontaneous Timed Ventilation – provides ventilation in synchrony with a person's spontaneous breathing efforts; triggering of a breath cycle is by the patient or the ventilator, should the person fail to trigger the ventilator after a preset time. In Spontaneous/Timed mode a "backup" rate is set to ensure that the patient still receives a minimum number of breaths per minute if they fail to breathe spontaneously.

Z_{rs} – total impedance of the respiratory system as measured by the forced oscillation technique (FOT) at a forcing frequency of 5 Hz.

X_{rs} – the reactance (i.e. the imaginary component of the impedance) of the respiratory system as measured by the forced oscillation technique (FOT) at a forcing frequency of 5 Hz.

ΔX_{rs} – is the difference between the mean value of X_{rs} during expiration (\bar{X}_{exp}) and the mean value of X_{rs} during inspiration (\bar{X}_{insp}). A breath is classified as flow-limited if its ΔX_{rs} is greater than 2.8 cmH₂O · s · L⁻¹

Background Information

Chronic Obstructive Pulmonary Disease (COPD) is a major cause of morbidity and mortality worldwide.

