1. Participants currently using a PAP or NIV device at home with a documented EPAP setting on their current device that is greater than then the mean or final EPAP determined during the therapy session of the screening visit.

Sub-Study Schedule of Events:

Sub-Study Screening Visit:

- All study participants will undergo the exact same study procedures as in study visit 1 in the primary study with the following differences:
 1. Study participants who are currently using an NIV or PAP therapy device at home that have a EPAP setting that is greater than the mean or final EPAP determined during the 20 minute therapy session will not be asked to continue onto the 2 week device home use period.
 2. Participants who are currently on NIV or PAP will not be scheduled for an overnight PSG.
 3. Once eligibility has been confirmed, participants will receive one on one training on the Vector NIV device and accessories by clinical study staff. They will also be given a device user manual. Once trained on the device, study participants will be asked to take the device home and use as instructed during the night for a 2 week period.

Sub-Study Office Visit:

Engineering Evaluation of the Vector NIV Device in Chronic Obstructive Pulmonary Disease (COPD) Patients

- At the end of the 2 week device home use period, study participants will be asked to return to the clinical study site to return the study Vector NIV device and complete a survey.

Unscheduled Sub-Study Visits:

Participants may be asked to repeat the two week take home portion of the study up to three (3) times. This will occur within three months of the sub-study screening visit.

Selection and Withdrawal of Subjects:

Inclusion Criteria

1. Age \geq 40 years of age; \leq 80 years of age
2. Ability to provide consent
3. Diagnosis of COPD
4. Must present with EFL via screening of the vector device at 3 cmH₂O
5. Have an EPAP to abolish EFL greater or equal to 6cmH₂O
6. Must be able to maintain SpO₂ greater than 88% at rest and during EPAP Titration

Exclusion Criteria:

1. Any major non COPD uncontrolled disease or condition, such as congestive heart failure, malignancy, liver or renal insufficiency (that requires current evaluation for liver or renal transplantation or dialysis), amyotrophic lateral sclerosis, or severe stroke, or other condition as deemed appropriate by investigator as determined by review of medical history and / or participant reported medical history

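### The rule for moving a home-NIV user onto Vector compares EPAP only, so it can clear a user for home nights on less pressure support or backup rate than prescribed

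*Combined protocol and SAP*

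**What the plan says.** The sub-study has two entry routes. One is for people who completed the initial study. The other is for people prescribed, and currently using, a PAP or NIV device at home who meet the primary eligibility criteria.

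For the second route, sub-study Exclusion 1 uses the screening visit to remove those with a "documented EPAP setting on their current device that is greater than then the mean or final EPAP determined during the therapy session". Difference 1 under Sub-Study Screening Visit repeats the test: users who "have a EPAP setting that is greater than the mean or final EPAP determined during the 20 minute therapy session" do not go on to home use. Difference 2 adds: "Participants who are currently on NIV or PAP will not be scheduled for an overnight PSG". Difference 3 says that, after training, "study participants will be asked to take the device home and use as instructed during the night for a 2 week period". Under Unscheduled Sub-Study Visits, "Participants may be asked to repeat the two week take home portion of the study up to three (3) times".

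The Glossary treats the other ventilator settings as separate from EPAP. It defines IPAP as "Physician prescribed pressure for the inspiratory (breathing in) phase of an individual on Bi-level PAP therapy". For S/T mode, it says that a backup "rate is set to ensure that the patient still receives a minimum number of breaths per minute if they fail to breathe spontaneously".

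Primary Exclusion 12 bars people in respiratory failure. It does not say whether that means acute or chronic, treated or untreated. The matching contraindication is equally unqualified.

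**The concern.** The sponsor saw that replacing a prescribed device needs a check that the new one does not deliver less, and wrote a rule for it. The rule covers only the setting that Vector uses against expiratory flow limitation (EFL). For a bilevel user, the ventilation delivered also depends on pressure support, or a target volume, and on the backup rate. Neither is in the rule.

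This matters because of who the route can recruit. The Background describes NPPV as an established option in hypercapnic respiratory failure due to COPD, and as something that may improve night-time hypoventilation. For a user with that indication, keeping EPAP while giving less support or no backup rate would still meet the EFL aim. It could also reduce the ventilation that the prescription was written to provide. The exposure is nocturnal, at home and repeatable.

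**Working it through.** The plan states no figure on this point, so the check sets the texts side by side, with one illustration.

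**1. What the rule tests.** Sub-study Exclusion 1 and screening difference 1 both exclude only if home EPAP > Vector EPAP (mean or final). IPAP, pressure support, target volume, mode and backup rate appear in neither.

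**2. When it passes.** Primary Inclusion 5 reads "Have an EPAP to abolish EFL greater or equal to" 6 cmH2O. If the comparator is the final EPAP, every home EPAP of 6 cmH2O or less passes automatically, whatever the rest of the prescription. The wording does not say whether the mean or the final value decides.

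**3. Is the result sensitive to support?** Pressure support = IPAP − EPAP. The documents give no home or Vector settings, so these values are assumptions: home device 22/6 cmH2O, so support is 22 − 6 = 16; Vector final EPAP 7.

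| Assumed Vector support (cmH2O) | Is 6 > 7? | Rule | Shortfall = 16 − Vector support |
|---|---|---|---|
| 4 | no | eligible | 12 |
| 8 | no | eligible | 8 |
| 12 | no | eligible | 4 |
| 16 | no | eligible | 0 |

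The rule gives the same answer in all four rows, and a change of backup rate would not alter it. The table shows that the rule does not respond to support. It says nothing about how often a shortfall occurs.

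**4. Do other readable safeguards compare delivered with prescribed ventilation?**
- Visit 1 titration: about 20 minutes, and the participant must stay awake. EPAP rises until EFL is abolished, and IPAP rises in proportion. The stated target is EFL, not the user's prescription.
- Gas exchange: SpO2 above 88% at rest and during titration. No CO2 measurement is mentioned.
- Study Visit 2: fixed pressure support and AVAPS are both tested, with a technician able to adjust settings. Home PAP and NIV users do not have this night.
- Sub-study endpoints: adherence, ventilator parameters and comfort. Neither SpO2 nor CO2 is named.
- Potential Risks and Discomforts: at home, the participant can remove the mask, and existing users are told to go back to their own device. This relies on a problem being noticed.
- Investigator discretion, the 30-day exacerbation exclusion and the medical history all help, but none compares settings.

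**5. Exposure.** One period is 2 × 7 = 14 nights. If the repeat wording means three periods in total, the ceiling is 3 × 14 = 42. If it means three repeats after the first, it is (1 + 3) × 14 = 56.

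**6. Who is affected.** Only users with bilevel support. By the Glossary, CPAP holds one pressure through both phases, so a CPAP-only user has no pressure support to match.

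**The case against.** The strongest objection is that the settings may be controlled where we cannot see. Appendix A is blacked out. Study Visit 1 cites it for the set-up of the EFL screening and titration procedure, and sub-study participants go through that same visit. Device training and a user manual follow. Any of these could set support and rate to the prescription. IPAP also rises with EPAP, and no readable text says that Vector lacks a backup rate. A reader might infer that NIV users will go home under-ventilated. The documents do not support that: the shortfall is permitted, not demonstrated.

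Second, Exclusion 12 and the contraindication are unqualified, and their plain wording could cover chronic treated failure. On that reading the users most at risk are never enrolled, and the route still has PAP users to recruit. A reader might infer that the plan knowingly admits patients in chronic failure. The text does not say so. It leaves the matter undefined, next to an Intended Use that covers respiratory insufficiency from COPD at home.

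Third, a reader might infer that low home minute ventilation could not be told apart from a lower setting or a device fault. That goes too far. The device outputs listed for the sleep study include IPAP, EPAP, leak and minute ventilation; the home parameter list is open-ended; and device deficiencies are logged separately.

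These points limit what can be claimed. They do not change the eligibility rule, which is fully readable, appears twice and names EPAP alone.

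**Conclusion.** The point holds as a gap in an eligibility rule. As written, the rule can clear a home bilevel user for 14 nights per period, with a ceiling of 42 or 56, whatever pressure support, target volume or backup rate was prescribed. No readable safeguard compares delivered with prescribed ventilation.

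The size of any shortfall and the number of NIV users cannot be derived from the documents, and the pressures in the illustration are assumptions. The conclusion rests on the readable text. If Appendix A or the training material already sets home support and rate from the prescription, what remains is to put that requirement into the rule itself. If Exclusion 12 is meant strictly, the safety stake is smaller, though other bilevel users would still be cleared on EPAP alone. This is a cheap improvement, not evidence of harm.

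**What to change.** For bilevel/NIV users only, not CPAP-only users:

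1. Extend sub-study Exclusion 1 and screening difference 1. Vector does not go home unless it is set to at least the prescribed pressure support or target volume and at least the prescribed backup rate, or the investigator records why less is acceptable. The investigator's note also covers cases where fixed support and a volume target cannot be compared directly.
2. At sub-study screening, record mode, IPAP or target volume, and backup rate from the same source as the documented EPAP.
3. Optionally, add a line to Exclusion 12 saying whether stable, chronic, treated respiratory failure counts.

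The cost is amendment wording in two or three places and a few extra fields. No visit, overnight study or CO2 test is added. The downside is that a few NIV users may not qualify for home use because Vector cannot reach their prescribed support; the documents do not allow that number to be estimated.
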